Study Protocol

Title: Utility of MRI with ultrasound gating for advanced fetal monitoring

Institution: This Hospital for Sick Children

Team Members

Principal Investigator: [name] (Imaging Scientist; SickKids)

Qualified Investigator: [name] (Cardiologist; SickKids)

Research Coordinator: [name] (Research Coordinator; SickKids)

Co-investigators: [name] (Scientist; University Medical Centre Hamburg-Eppendorf)

[name] (Research Analyst; SickKids)

[name] (Postdoctoral Fellow; SickKids)

[name] (Ph.D. Student; University of Toronto)

[name] (Ph.D. Student; University of Toronto)

Study Period: 1 year

BACKGROUND AND SIGNIFICANCE

Abstract

This is a pilot study involving simultaneous magnetic resonance imaging (MRI) and ultrasound in pregnant participants with fetal congenital heart disease. The aim of this research study is to integrate non-imaging Doppler ultrasound to provide fetal cardiac gating during the MRI acquisition. This aim encompasses making clear images of the fetal heart and blood vessels, and reproducible measurements of fetal blood flow. MRI-derived blood flow waveforms in the fetus and anatomical images of the fetal heart will be compared with those from diagnostic ultrasound for validation.

Rationale

Fetal MRI can be used in adjunct to conventional obstetric ultrasound to assess and monitor the health of the fetus in the case of complicated pregnancies. For example, once the fetus is diagnosed with congenital heart disease (CHD) through initial ultrasound screening, the patients may be referred to our MRI program for additional fetal cardiovascular assessment. We would like to develop and apply MRI for advanced fetal cardiovascular assessment to better manage complicated pregnancies with the intent to improve patient care and postnatal health outcomes. Results from MRI may aid in the guidance of fetal interventions, managing optimal timing of delivery and planning for post-natal care.

Our group has studied the fetal circulation in healthy pregnancies and in the settings of CHD and intrauterine growth restriction (IUGR) [1]. Despite our early successes in studying the fetal heart and circulation by MRI, such studies have been limited by practical challenges including the small size of fetal structures, the high fetal heart rate and unpredictable motion of the fetus. For example, in late gestation the diameter of a normal left ventricle is only 15 mm and major vessels are even smaller with diameters less than 8 mm [2]. These small dimensions coupled with high heart rates (between 110-180 bpm) necessitate high spatial and temporal resolutions to capture cardiac dynamics [3].

To address these limitations, state-of-the-art MRI techniques originally designed for evaluating the adult heart must be translated to fetal imaging [4]. Phase contrast (PC) MRI is the gold standard for non-

invasive measurement of blood flow in post-natal subjects. Cardiovascular anatomical MRI is an essential diagnostic tool in the evaluation of the heart post-natally. It is non-invasive, provides excellent soft tissue contrast and has the ability to perform multi-planar imaging in any orientation. PC MRI and anatomical MRI of the heart necessitate synchronization of image acquisition with the cardiac phase, which is most often facilitated by an electrocardiogram (ECG) signal.

In the case of fetal cardiovascular complications such as CHD, evaluation of the fetal heart is important for guiding treatment of disease, timing of delivery, and planning appropriate care after birth. Detection of the fetal heart beat through ECG has been done by placing electrodes on the mother's abdomen. Even after decades of developments in fetal ECG, detection of the fetal heart beat through ECG has been shown to be fundamentally unreliable due to the relatively small electric potentials generated from the fetal heart, interference from other potentials generated by the mother, and shielding from many layers of tissue [5]. A very low conductivity layer of tissue called the vernix caseosa which forms around the fetus between the 28th and 32nd weeks of gestation, makes detection of an fetal ECG signal particularly difficult [5]. Lack of an available ECG signal from the fetus necessitates the use of novel cardiac gating techniques for MRI. For this, we propose to investigate the use of an MRI-compatible Doppler ultrasound probe to produce a gating signal from the fetal heart. The Doppler ultrasound probe detects blood flow through the fetal heart, which can be used to trigger MRI data acquisition and produce dynamic images of the fetal heart. Our collaborators have successfully used this technique to produce a cardiac gating signal for MRI gating in non-pregnant adult humans [6], fetal humans [7], and fetal sheep [8].

This study will be conducted in compliance with this research protocol, GCP guidelines and with the Hospital for Sick Children's regulatory requirements.

Significance

Cardiac gated fetal MRI methods will enable accurate assessment of fetal cardiovascular function and development. The prospective gating provided by the Doppler ultrasound probe will allow direct translation of postnatal MRI techniques to the evaluation of pathologies like fetal heart disease and intrauterine growth restriction, to better guide treatments such as early delivery and to plan appropriate care after birth.

Hypotheses/Research Questions

Our proposal is geared toward method development and validation of MRI scanning techniques. We will compare dynamic cardiac images and blood flow patterns obtained using prospectively gated MRI with those obtained using conventional diagnostic ultrasound imaging. We will also compare MRI measurements made with the newly developed prospective gating method to un-gated and retrospectively gated MRI.

Our primary objective is to assess the feasibility of using Doppler ultrasound gated MRI for advanced fetal monitoring, which would include understanding the relationship between maternal-placental-fetal cardiovascular physiologies in utero. To achieve the primary objective, the following foundational objectives need to be accomplished:

- (1) Incorporate fetal gating information from a novel Doppler ultrasound probe into our existing MRI pulse sequences and reconstruction software

- (2) Validate Doppler ultrasound gated MRI by comparison to MRI images created without gating information from the Doppler ultrasound probe, in addition to measurements made with clinical ultrasound
- (3) Assess utility of prospective Doppler ultrasound gating for fetal MRI compared to un-gated and retrospectively gated fetal MRI

Procedures

Pregnant volunteers carrying a fetus affected by congenital heart disease who are scheduled for a clinical fetal ultrasound examination at the Fetal Echocardiography Clinic at SickKids will be invited to undergo an MRI, where MRI techniques incorporating Doppler ultrasound gating will be tested.

Participants will be scanned with the Siemens Prisma^{FIT} or Siemens Magnatom Skyra, both which are 3T MRIs at SickKids. We will enroll 20 pregnant volunteers (10 in the 2nd trimester and 10 in the 3rd), allowing for method development and testing at different gestational ages, providing more dramatic variation in anatomy and vessel size and more variation in the types and magnitude of fetal motion. During scanning, pregnant mothers will be asked to remain still for periods of time on the order of 5 minutes as pulse sequences are run.

The Doppler ultrasound fetal gating device, which will be placed on the patient's abdomen by a registered MRI technician and held in place with a flexible elastic band, will be connected to the gating input of the MRI for either the entirety of, or a portion of the MRI examination. As is the case with all clinical ultrasound examinations, a water-based gel will be applied to the mother's skin below where the gating device is placed. Foam padding will be placed around the transducer cable to shield from possible heating of the cable. The gating device will detect when each fetal cardiac cycle begins and trigger MRI acquisition. MRI examinations will be up to 60 minutes in length. The MRI examination will be scheduled on the same day that volunteers have their clinical ultrasound appointment, with both examinations occurring within the shortest time-period that can reasonably be achieved.

Data Collection / Analysis

Anatomic MR images of the fetal heart (be they single or multi-slice), phase-contrast MR images of blood flow in great fetal vessels, and T1 and T2 maps in great fetal vessels will be acquired using prospective gating information from the Doppler ultrasound probe. Similarly, anatomical images, phase contrast images, and T1 and T2 maps will be acquired without any gating input. From the ultrasound examination during the patient's visit to the Fetal Echocardiography Clinic, we will retrieve anatomical images of the fetal heart in addition to flow waveforms acquired in the great fetal vessels.

MR data acquired without the Doppler ultrasound gating signal will be reconstructed without any gating information, and will also be reconstructed using retrospective gating techniques that we have previously developed [9], [10]. Anatomic MR images will be compared quantitatively in terms of myocardial border sharpness, with the anticipated result that Doppler gated MR will show higher border sharpness than un-gated or retrospectively gated MR. Ejection fraction will be calculated from anatomical cardiac images. These estimates of ejection fraction will be compared to ejection fraction calculated from the ultrasound images, with the anticipated result that Doppler gated MR will agree better with ultrasound images than un-gated or retrospectively gated MR.

T1 and T2 maps will be compared in terms of the standard deviation of T1/T2 values in ROIs placed in the larger great fetal vessels, with the anticipated result that Doppler gated MR will provide a tighter distribution than un-gated or retrospectively gated MR. From the ungated, retrospectively gated, and Doppler ultrasound gated cardiac images, we will calculate *ejection fraction*.

Flow waveforms in great fetal vessels derived from retrospectively gated and Doppler ultrasound gated phase contrast images will be compared to flow waveforms measured with clinical Doppler ultrasound during the patient's visit to the Fetal Echocardiography Clinic (which we view as a gold standard). We anticipate that flow waveforms derived from Doppler ultrasound gated MR will prove to be more similar to the gold standard than flow waveforms derived from retrospectively gated MR.

Once enrolled, participants will be assigned a study number and all data and images gathered from the study procedures will be de-identified so to be identifiable only by this number and not any personal health information. Results of this study will be published in conference presentations and proceedings, peer reviewed journals, and academic rounds.

Inclusion and exclusion criteria

Inclusion criteria:

- pregnant adults (age 18 and up) with fetus affected by congenital heart disease
- singleton pregnancy in their 2nd and 3rd trimesters
- scheduled for a clinical fetal ultrasound examination at the Fetal Echocardiography Clinic at SickKids

Exclusion criteria:

Exclusion criteria that prevent the mother from having an MRI

- claustrophobia
- cardiac pacemaker
- non-MRI compatible implants

Other exclusion criteria

- non-singleton pregnancy
- obesity (BMI > 30)

Possible harm to the patients:

Fetal MRI has been used for more than 25 years and poses no risk to the fetus in the 2nd and 3rd trimesters of pregnancy [11]. MRI does not use ionizing radiation, which is known to be harmful to the fetus, and risks are primarily related to the rise in body temperature due to absorption of radio-frequency energy. The UK National Radiological Protection Board suggests that MRI be restricted to the 2nd and 3rd trimester because of theoretical concerns about teratogenesis with MRI in early pregnancy [12], however recent studies of incidental MRI use in 1st trimester pregnancies have demonstrated no increase in adverse outcomes in these cases when no MR contrast agent is used [13]. In fetal MRI, current data and research studies have failed to demonstrate any reproducible harmful effects on pregnant women and their fetuses at magnetic field strengths of 3T or less [14]. The *International Commission on Non-Ionizing Radiation Protection* concludes that "adverse developmental effects [on the fetus] will be avoided with a margin of safety if the body temperature of pregnant women does not rise by more than 0.5 °C and the temperature of the fetus is less than 38 °C" [15].

MRI manufacturers have adapted the *International Electrotechnical Commission* (IEC) standard IEC 606-1-2-33, which defines three levels of MRI RF exposure risk. The lowest risk level, *normal mode*, sets a maximum specific absorption rate (SAR) of 2 W/kg and a maximum temperature rise of 0.5 °C. Before any MR pulse sequence is run, an estimate of whole-body SAR and temperature rise is made, which accounts for the patient's height, weight, ambient temperature and humidity, and details of the MR pulse sequence. When operating in normal mode, the scanner will simply not run a pulse sequence if the estimated SAR or temperature rise exceeds the thresholds defined by IEC normal mode. It is known that the fetal temperature rests ~0.5 °C above the maternal body temperature (which is 37 °C) due to limited pathways for heat transfer [16]. Numerical simulations suggest that fetal temperature will not pass 38°C when a mother is scanned in *normal mode* [16], giving assurance that we will operate within internationally recognized safety limits.

Concerns related to the loud noises generated by the MR coils and their potential to cause acoustic damage to the fetus have been dispelled by several studies [11].

In addition to the ultrasound that volunteers will undergo to validate our MRI techniques, ultrasound is the enabling technology behind the Doppler ultrasound probe used for fetal cardiac gating. Doppler ultrasound detects blood velocity by transmitting acoustic waves into the patient and then detecting waves that reflect back from moving red blood cells. Ultrasounds are included in routine prenatal care around the world and no harmful effects have ever been detected. Theoretical concerns are related to tissue heating (as in MRI) in addition to ultrasonic gaseous cavitation [17]. The Doppler ultrasound probe will be built by our collaborators from the Department of Diagnostic and Interventional Radiology at the University Medical Centre in Hamburg, Germany where they have received ethics approval for use in non-pregnant adult human volunteers [6] and later, for fetal imaging in pregnant adult volunteers [7]. The transducer transmits acoustic energy at a maximum (pulse averaged) power of 1.5 mW/cm², which is well below the limit of 20 mW/cm² set by Health Canada for Doppler ultrasound based fetal heart rate monitors [18].

This study will not proceed before we receive Health Canada approval to use this new medical device.

It is known that use of ultrasonic gels carries a small risk of spreading bacterial infections [19]. Health Canada mandates that sterile gels be used in all procedures that pass a device through tissue (such as ultrasound guided tissue biopsy) or where the ultrasound transducer makes contact with a mucus membrane. Because we will only put the ultrasound gel on intact skin, there is minimal risk of spreading infection. The ultrasound transducer will be cleaned with an antibacterial disinfectant after each use, and Health Canada guide-lines regarding use of non-sterile ultrasound gels, as outlined in [20] will be followed.

The device manufacturer reports that in rare circumstances, the cable that connects to the transducer can heat to up to 70 °C. They have insulated the cable with foam padding. With the insulation attached, the surface temperature of the cable will not exceed 43 °C. Since the cable can make contact with the participant's skin, this may cause minor discomfort.

Any adverse events (such as injury during MRI examination) will be reported to the SickKids Research Ethics Board.

Possible benefit to the patient:

Fetal cardiac MRI provides a way of making pictures of the fetus, in addition to conventional ultrasound screening, and may result in visualization of previously undetected abnormalities. The probability of such benefits to the patients is very small because such abnormalities would likely have been detected by ultrasound during normal standard of care. In such a situation, [name], who is in the patient's circle of care, will be informed of the findings and will take appropriate action.

Possible benefit to society:

Fetal cardiac MRI methods will enable more accurate assessment of fetal cardiovascular function and development. The imaging techniques provided by the methods we develop will allow for early evaluation of fetal heart and/or placental disease to better guide treatments such as early delivery and to plan appropriate care after birth.

Data collection and storage:

The source images from the study will be de-identified and stored on the secure hospital research PACS system with password-protected access. The de-identified data will be associated with a code, and the key-code will be stored in password-protected files on an internal hospital directory. The data will be destroyed after a period of 7 years. De-identified MRI and ultrasound data will be shared with our collaborator ([name]) at the University Medical Centre Hamburg-Eppendorf in Hamburg, Germany. Data will be transferred using the SickKids RIT-FTP service. Only the study team identified will have access to the patient data.

Withdrawal from study participation:

Participants can withdraw from the study at any point, for any reason, specified or unspecified, without penalty. No new data will be collected or linked to other data from that point on. Upon request any processed and unprocessed data can be destroyed.

Research budget and funding:

The main cost of this study is the cost of the MRI examinations, which are \$500 per hour. Each participant will be reimbursed for travel and parking, costing up to \$33.50. We will pay to make our publications open access, for which we will allocate \$2000. The total cost of this project could reach \$12,670. A total sum \$30,000 is available through CIHR funding.

References

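### Must the protocol fix the gated MRI acquisition before the same 20 participants are used to validate it?

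*Protocol*

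**What the plan says.** The Abstract calls this a pilot study, and Hypotheses/Research Questions says the proposal aims at both developing and validating scanning methods. The primary objective is feasibility. Three foundational objectives sit beneath it:

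- Objective 1: "Incorporate fetal gating information from a novel Doppler ultrasound probe into our existing MRI pulse sequences and reconstruction software".
- Objective 2: "Validate Doppler ultrasound gated MRI by comparison to MRI images created without gating information from the Doppler ultrasound probe", and by comparison with clinical ultrasound measurements.
- Objective 3: "Assess utility of prospective Doppler ultrasound gating for fetal MRI compared to un-gated and retrospectively gated fetal MRI".

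Procedures describes a single group of 20 participants, 10 in the second and 10 in the third trimester, "allowing for method development and testing at different gestational ages". The sentence goes on to justify the split by the variation in anatomy, vessel size and fetal motion that it brings.

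Data Collection / Analysis plans gated and un-gated acquisitions. The un-gated data are reconstructed without gating and "will also be reconstructed using retrospective gating techniques that we have previously developed". It states expected directions of result but no hypothesis test, error rate or power.

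The only start condition is for the device (Possible harm to the patients): "This study will not proceed before we receive Health Canada approval to use this new medical device".

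**The concern.** The comparison looks uneven. Hypotheses/Research Questions announces: "We will also compare MRI measurements made with the newly developed prospective gating method to un-gated and retrospectively gated MRI". The retrospective comparator existed before the study, whereas the gated method is to be integrated and tested in the same people who supply the validation data. There is no lead-in, no division into development and validation scans, and no point at which pulse sequence, trigger settings and reconstruction are final.

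If settings changed during enrolment, the error could run either way. Choosing settings on the participants who are then compared would flatter the gated method. Pooling early, immature scans with later ones would understate it. In both cases a result over all 20 might not describe one identifiable technique. A prospectively triggered scan cannot be repeated with better settings once the visit is over, so the point seems to belong in the protocol and not in a later analysis plan.

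**Working it through.** The protocol gives no alpha, power, effect size or standard deviation, and 20 is stated without derivation, so there is no planned figure to reproduce. The check is mainly one of reading, with some arithmetic on the cost of a lock.

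**1. Is a change of settings described?** No. The clause in Procedures does use the word development, but its job there is to explain the 10 + 10 split by trimester. No section describes revising the acquisition from one participant to the next, and none says that different versions will be pooled.

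**2. How much room is there for versions to differ?** Less than the word development suggests. Objective 1 feeds a signal into sequences the group already has. Procedures says the device plugs into the scanner's gating input and triggers on each fetal cardiac cycle. The Rationale reports that collaborators have already used the technique in adults, human fetuses and fetal sheep. Two details might look like open settings: the device may be connected for only part of the examination, and anatomic images may be single- or multi-slice. The first fits the plan to acquire some data without gating; the second concerns coverage. None of this proves that the acquisition is fixed at the start, but material drift remains conjecture.

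**3. Would optimistic selection fit the visit?** The simplest selection model needs participants to receive several gated settings, with the best chosen on the outcome measures. Procedures caps the examination at 60 minutes and mentions periods of stillness of about 5 minutes. Assume 5 minutes per acquisition and four data types (anatomic, phase contrast, T1, T2):

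- One gated setting plus un-gated: (4 × 1 + 4) × 5 = 40 minutes.
- Two gated settings: (4 × 2 + 4) × 5 = 60 minutes, the whole slot.
- Five gated settings: (4 × 5 + 4) × 5 = 120 minutes, twice the slot.

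On that assumption, extensive within-participant tuning does not fit. Changing settings between participants would fit, but the best-of-several model does not describe it. The protocol supplies nothing from which to size that effect.

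**4. What would a lock cost?** The 95% confidence half-width for a mean paired difference, in SD of that difference, is t(0.975, n − 1)/√n:

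| Participants after the lock | Half-width (SD) | Ratio to n = 20 |
|---|---|---|
| 20 | 0.468 | 1.00 |
| 18 | 0.497 | 0.497/0.468 = 1.06 |
| 16 | 0.533 | 0.533/0.468 = 1.14 |

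A lock before the first participant costs no precision, but it commits the team before the range of gestational age and fetal motion has been seen.

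**5. Could a later analysis deal with it?** Largely. Restricting a comparison to the final version, or reporting by version, is an analysis decision and needs only a record of the settings used. Reconstruction is not tied to the visit as triggering is. The protocol itself plans two reconstructions of the un-gated data, and nothing rules out one final reconstruction for all gated data, provided the raw data are kept. Only the acquisition is irreversible.

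**The case for a change.** The best argument for a change is that Procedures assigns development to the enrolled participants themselves. The order of the objectives is not a completion point, and the collaborators' experience does not fix this site's sequences. The group expects sharper myocardial borders, better ejection-fraction agreement, tighter T1/T2 distributions and closer flow waveforms, and it intends to publish. Such claims should attach to an identifiable version. Pairing within participants protects against differences in case mix, but not against settings being chosen on the validation data. Nor does a confidence interval cover that kind of bias. One sentence and a version entry per participant would be cheap, and a version record cannot always be rebuilt afterwards.

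Much of this stands. No lock point is stated, and no section requires the version to be recorded. What does not follow is that the plan is in error. The harm depends on an event the protocol never announces, it touches only the comparisons under objectives 2 and 3, and most of the remedy is analytic. The part that is not analytic, when to stop adjusting, is a judgement in a pilot of 20 whose stated purpose includes development. Reasonable statisticians would differ on it.

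**Conclusion.** No change is needed. The protocol leaves a detail unstated within a design it declares openly. The primary feasibility objective is little affected. The possible bias in the objective 2 and 3 comparisons cannot be sized from the protocol and is zero if the gated acquisition stays the same throughout. A compulsory lock would trade that conditional risk for the risk of fixing the method too early, or for an interval about 6% wider with 18 participants after the lock and 14% wider with 16. That is a fair trade-off for the investigators to settle.

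This conclusion assumes that the settings used for each participant can be recovered, so that results can be reported by version, or for the final version, if the acquisition did change. A simple log of acquisition and trigger settings, and one final reconstruction for all gated data where possible, would secure that. Both are good practice and optional. The conclusion would weaken if the comparisons were presented as confirmatory, which the protocol does not do.

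### Does comparing ejection fraction with un-gated MRI make the Doppler-gated result look more accurate than it is?

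*Protocol*

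**What the plan says.** The Data Collection / Analysis section describes the comparator data: "MR data acquired without the Doppler ultrasound gating signal will be reconstructed without any gating information, and will also be reconstructed using retrospective gating techniques". EF is then to be taken from the anatomical images and compared with ultrasound EF, "with the anticipated result that Doppler gated MR will agree better with ultrasound images than un-gated or retrospectively gated MR". A later sentence in the same section confirms that all three image types are used: "From the ungated, retrospectively gated, and Doppler ultrasound gated cardiac images, we will calculate" EF. No frame duration is given for the un-gated series.

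The third foundational objective (Hypotheses/Research Questions) is to "Assess utility of prospective Doppler ultrasound gating for fetal MRI compared to un-gated and retrospectively gated fetal MRI". The second is to validate Doppler-gated MRI against both MRI made without the Doppler signal and clinical ultrasound measurements.

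The Rationale states that "PC MRI and anatomical MRI of the heart necessitate synchronization of image acquisition with the cardiac phase", and of the fetal heart that "These small dimensions coupled with high heart rates (between 110-180 bpm) necessitate high spatial and temporal resolutions to capture cardiac dynamics". The flow analysis has only two MRI arms: "Flow waveforms in great fetal vessels derived from retrospectively gated and Doppler ultrasound gated phase contrast images will be compared" with clinical Doppler ultrasound.

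**The concern.** EF is (EDV − ESV)/EDV, where EDV and ESV are the end-diastolic and end-systolic volumes. An image that averages over whole beats shows one blurred volume, so EDV = ESV and EF is zero or undefined. The Rationale says that cardiac MRI needs synchronization, and the phase-dependent flow comparison omits un-gated MRI, so a reader may infer that the un-gated series cannot yield a usable EF. Beating it would then show only that Doppler gating separates cardiac phases at all. If that win were reported as agreement with ultrasound, a poorly performing trigger could pass as validated.

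**Working it through.** **Inputs from the Protocol.** Fetal heart rate 110-180 bpm (Rationale); 20 participants (Procedures). The Protocol gives no EF standard deviation, agreement limit, power or frame duration, so there is no stated figure to reproduce.

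**Assumptions.** True EF 60% (EDV 100, ESV 40, mean volume 70) with a raised-cosine volume curve. Error SDs in EF points: ultrasound 7, Doppler-gated 10, whole-beat un-gated 7, retrospectively gated 10, time-resolved un-gated 10. Errors are normal and independent. Tests are two-sided at 5%.

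**1. Un-gated EF by temporal window.** The beat length is RR = 60000/bpm: 60000/110 = 545 ms and 60000/180 = 333 ms. Averaging over a window W multiplies the cosine amplitude (30) by s = |sin(πW/RR)/(πW/RR)|, so EF = 60s/(70 + 30s).

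| Window | 110 bpm | 180 bpm |
|---|---|---|
| 50 ms | 59.4% | 58.4% |
| 100 ms | 57.7% | 53.8% |
| 200 ms | 50.7% | 35.6% |
| 300 ms | 39.4% | 8.9% |
| one beat | 0% | 0% |

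For example, at 180 bpm and 100 ms, s = 0.858 and EF = 51.5/95.8 = 53.8%. The un-gated contrast is therefore meaningful with a short window and empty with a whole-beat one.

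**2. A faulty Doppler trigger.** If a fraction f of triggers falls at random phases, the volume curve becomes (1 − f)V(t) + 70f.

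- f = 0.25: (92.5 − 47.5)/92.5 = 48.6%, 11 points low.
- f = 0.50: (85 − 55)/85 = 35.3%, 25 points low.
- f = 0.75: (77.5 − 62.5)/77.5 = 19.4%, 41 points low.

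**3. How often that faulty Doppler EF is closer to ultrasound than the comparator (simulation, per fetus).**

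| f | un-gated EF 0-10% | un-gated, time-resolved (56%) | retrospective (60%) |
|---|---|---|---|
| 0.25 | over 99% | 39% | 38% |
| 0.50 | 98-100% | 14% | 14% |
| 0.75 | 78-94% | 2% | 2% |

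The 56% is the EF for a 100 ms window at 145 bpm. The whole-beat column shows the concern is real if that column applies. The retrospective column shows that the other half of the same sentence exposes the fault.

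**4. The direct comparison with ultrasound.** The SD of Doppler minus ultrasound EF is √(10² + 7²) = 12.2, and its standard error with 20 fetuses is 12.2/√20 = 2.73.

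- An 11.4-point bias gives a noncentrality of 11.4/2.73 = 4.2 and a paired t-test power of about 98%.
- A 24.7-point bias gives 24.7/2.73 = 9.0, and a 40.6-point bias gives 14.9. Power is about 100% for both.
- With wider SDs (ultrasound 10, Doppler 15), the standard error is 18.0/√20 = 4.03, and power is about 76%, 100% and 100%.

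**The case for a change.** The strongest case for a change is that the un-gated EF contrast is written into the plan, feeds the validation and utility objectives, and comes with an expected answer that a whole-beat series would guarantee. It is listed beside retrospective gating as an agreement comparator and is not labelled a negative control. Stating the window would cost a line of text. Even a time-resolved series carries a built-in EF loss, about 2-6 points at 100 ms and 9-24 points at 200 ms, that a reader should know.

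It stands that the window is not given and that a whole-beat contrast would say little about accuracy. The inference that the series is whole-beat does not stand:

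- Reconstruction without gating information means no cardiac synchronization. It does not mean averaging over time.
- The synchronization sentence in the Rationale closes a paragraph on techniques established after birth.
- The Procedures say that "pregnant mothers will be asked to remain still for periods of time on the order of 5 minutes as pulse sequences are run". That describes how long the mother keeps still, not how long one image averages.
- Leaving un-gated MRI out of the flow comparison while naming it twice for EF fits equally well with investigators who expect un-gated anatomical images to yield an EF.

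**Conclusion.** No change is needed. The weakness exists only if the un-gated series averages over whole beats, which the Protocol does not state. Even then, the planned analyses reach a sound conclusion. The direct comparison with ultrasound detects an 11-point Doppler bias in about 98% of trials (about 76% with the wider SDs) and a 25-point bias in practically all. The anticipated result, read whole, would fail against retrospective gating. To mislead, a report would have to quote half of one sentence and leave out two planned comparisons.

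The un-gated arm is also a fair baseline. The third objective asks for it, this is a pilot feasibility study, and the sentence states an expectation rather than a success criterion. It retains some value as a negative control: with wholly random triggers, Doppler EF is closer to ultrasound than the whole-beat EF in at most 50% of fetuses. The frame duration is an acquisition detail that analysts will have when they measure EF and can report beside it.

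The sizes rest on the assumed true EF of 60%, the cosine curve, the SDs and the misfire fractions, none of which the Protocol gives. The conclusion rests mainly on which comparisons are planned.
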